- An application for waiver/alteration of HIPAA authorization will be submitted

APPENDIX – Data Collection Variables

Was the patient ALREADY receiving intravenous fluid bolus?	Yes/no
Estimated volume of fluid bolus infused before meds (mL)	Volume
Induction/sedation and total doses	Etomidate Ketamine Ativan Versed Morphine Fentanyl Propofol Other (free text) None
Post-intubation sedation	Etomidate Ketamine Ativan Versed Morphine Fentanyl Propofol Other (free text) None
Gender	Male/female
Body Mass Index (BMI)	Numeric
Self-identified race (from medical record)	White Black/African American Asian American Indian or Alaska Native Native Hawaiian or Other Pacific Islander
Chronic respiratory comorbidities	Asthma COPD Cystic fibrosis Interstitial lung disease Malignancy Neuromuscular weakness Obstructive sleep apnea Pulmonary hypertension Recurrent aspiration Other (free text)
Chronic non-respiratory comorbidities	Atrial fibrillation Cerebrovascular accident Chronic kidney disease Cirrhosis Congestive heart failure Coronary artery disease Diabetes mellitus End-stage renal disease Hypertension Malignancy, leukemia or lymphoma active Solid organ transplant stem cell transplant Bone marrow transplant

	Spinal CORD injury Traumatic brain injury Other (free text)
Primary admit diagnosis	Trauma/non-trauma
Active neurologic conditions at the time of intubation	Altered mental status Intracranial hemorrhage Cord compression or epidural abscess Meningitis or encephalitis Myasthenic crisis Seizure or status of left against Stroke traumatic brain injury
Active cardiac conditions at the time of intubation	Cardiac arrest Cardiogenic permanent edema Congestive heart failure Echogenic shock Hypertensive urgency or emergency Myocardial infarction
Active pulmonary conditions at the time of intubation	Acute respiratory distress syndrome Asthma Aspiration COPD Hypercarbic respiratory failure Hypoxemic respiratory failure Pneumonia Upper airway obstruction
Active gastrointestinal conditions at the time of intubation	Acute liver failure Bowel obstruction Bowel perforation Gastrointestinal bleeding Hepatorenal syndrome Pancreatitis
Prior to intubation, had the patient received ketamine or etomidate during this hospitalization (during a previous procedure or intubation)	Ketamine Etomidate
Was the patient on corticosteroids at the time of enrollment?	Yes/no
Vasopressors or inotropes in the hour prior to enrollment?	Yes/no
Which vasopressor or inotrope?	Epinephrine Norepinephrine Phenylephrine Dopamine Dobutamine Milrinone Angiotensin II
Was the patient on BIPAP or HFNC for respiratory failure in the 1 hour prior to enrollment (excluding pre-oxygenation)?	Yes/no
Was the patient on BIPAP or HFNC for respiratory failure in the 1 hour prior to enrollment (excluding pre-oxygenation)?	Optiflow, Vapotherm

Highest FIO2 delivered in the 1 hour prior to enrollment (excluding preoxygenation for the procedure).	For patients on nasal cannula, use estimation that $FIO_2 = 0.21 + 0.03^*(LPM\ of\ NC\ O_2)$
Neuromuscular Blockers	Rocuronium Vecuronium Succinylcholine Cisatracurium Other None Unknown
Total dose of each agent given peri-intubation	Numeric
Initial laryngoscope device type	Free text
Difficult airway characteristics (active at the time of intubation)	Vomiting Witnessed aspiration Upper GI bleeding Epistaxis or oral bleeding Upper airway mass, infection, trauma Head and neck radiation Obesity, BMI greater than 30 Limited neck mobility Limited mouth opening History of OSA Other, free text
Vital signs at 24 hours	Systolic blood pressure Diastolic blood pressure SPO2 FiO2 PEEP
Vasopressors or ionotropes used at 24 hours after intubation?	Epinephrine Norepinephrine Phenylephrine Dopamine WB Milrinone Angiotensin II
Is a chest x-ray available between intubation and 48 hours after intubation?	Was a NEW pneumothorax present on the first chest x-ray obtained in the first 48 hours after intubation? Is there evidence of new pneumonia? Yes/no
Cardiac arrest within 1 hour of intubation?	Yes/no
Death within 1 hour of intubation?	Yes/no
Did the patient die before discharge from the hospital?	Yes/no
Duration of mechanical ventilation (days)?	Number of days from study intubation until achieved final unassisted breathing during this hospitalization or death. Note: After extubation, a reintubation for less than 24 hours and for the purpose of a procedure will not count as a ventilator day. Information censored at hospital discharge. IGNORE data from outpatient records or readmissions.
Did the patient die in the ICU?	Yes/no
Duration of mechanical ventilation (days)?	Numeric
Duration of vasopressor support (days)	Numeric

ICU length of stay (days)	Numeric
---------------------------	---------

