Clinical Rotating Protocol	Currently in our emergency department, there are multiple VL devices that are already in use. These devices include the i-view as well as multiple reusable VL devices such as the GlideScope and the Storz C-Mac system. To ensure that we get high quality data, we are seeking to implement a clinical rotating protocol in which we will alternate months. For the clinical rotating protocol, one month will be the i-view and the next month will be the durable VL devices (e.g. January will be i-view, February will be the durable VL devices). As part of the clinical rotating protocol, we will place clinician-facing signage to the clinician work areas, on the airway boxes, and on the equipment in the department indicating which device is for that month if choosing to participate in the study. During the i-view month we may use a colored bag over the durable VL devices. Of note, our devices are routinely covered in a protective bag to keep it clean when not in use (e.g. aerosolized COVID, etc.) During the durable VL month we will place signs on the i-view device indicating that it is not an i-view month. We will use educational reminders to the staff about the protocol schedule and the purpose of the study throughout. We must note, however, the devices will remain in the department should the attending clinician need to break the protocol and obtain any of the devices. We will ensure that clinicians are able to access any of the equipment that they may want to utilize easily during emergent situations.
Data Collection	Data will be collected using the standardized data collection form that gathers routine healthcare data in a standardized form and ensures that the study team can identify intubations that occur. That information will then be linked to patient outcome data extracted by study team members.

B5.4 Data Collection

Data Element/Variable	Source	Operational Specific
Demographics, procedural data, complications, procedural operator data	Case report form	The data will be extracted into a Microsoft Excel database
Outcome data – Please see data variable collection appendix listed below	Case report form/T-system/trauma flow sheets/AHLTA/Impax/Essentris/MHS	The data will be extracted into a Microsoft Excel database

B5.5 Managing Data and/or Human Biological Specimens for this Research

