5.7.1.3 Any device not approved by the FDA

N/A – This section is not applicable.

B5.7.2 Drugs

B5.7.2.1 FDA-approved and used in accordance with the approved labeling

N/A – This section is not applicable.

B5.7.2.2 FDA-approved and used in a manner not in accordance with its approved labeling

N/A – This section is not applicable.

B5.7.2.3 Any drug not approved by the FDA

N/A – This section is not applicable.

B8 Statistical Analysis

B8.1 Sample Size Estimation

A power analysis in SAS version 9.4 (SAS Institute, Cary, NC) indicated that a total sample of 122 would be needed to find that the i-view is non-inferior to the reusable VL if the expected outcome rate (proportion of patients experiencing first-pass success) for the i-view is 87%, the expected outcome rate for the reusable VL is 92%, the noninferiority margin is 5%, power is 80%, and alpha is 5%.

B5.8.2 Data analysis

We will use the Farrington-Manning score test for non-inferiority to test the first two hypotheses (that the i-view has a non-inferior proportion of patients experiencing hypoxic events, and that the i-view has a non-inferior first-pass success rate compared to the reusable VL devices). The Farrington-Manning score test computes the proportion (risk) difference and 90% confidence interval (for a one-sided test) with regards to a predetermined non-inferiority limit. We will use pairwise deletion to handle missing data points (i.e., will only exclude observations if missing data relevant to the specific analysis). Moreover, we may perform regression modeling to adjust for confounders. We performed all statistical analysis using Microsoft Excel (version 10, Redmond, Washington) and JMP Statistical Discovery from SAS (version 13, Cary, NC) or another available commercial software package. We will present continuous variables as means and 95% confidence intervals, non-parametric continuous variables and ordinal variables as medians and interquartile ranges, and nominal variables as percentages and numbers. Significance will be set at $p=0.05$. We will compare binomial variables using the Chi-square test, normally distributed continuous variables using the Student's t-test, and non-parametric and ordinal variables using the Wilcoxon Rank sum test.

SECTION C: HUMAN RESEARCH PROTECTIONS

C1. RECRUITMENT AND CONSENT

C1.1 Identification and Selection of Subjects

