Whenever appropriate, the subjects will be provided with additional pertinent information after participation.

Many of the patients that we are intubating are critically ill and not expected to survive. As such, it would be impractical to attempt to provide them with information on a procedure that occurred as part of their routine clinical care.

C1.4.4 Research involving a waiver of the requirement for investigator to obtain a signed consent form

N/A – This section is not applicable.

C1.4.5 Waivers of assent or parental permission when the research involves children

N/A – This section is not applicable.

C1.4.6 Research involving data collection for the USAMRDC Volunteer Registry Database

N/A – This section is not applicable.

C2. COMPENSATION FOR PARTICIPATION

Patients will not be compensated for participation as we are only collecting data in conjunction with routine clinical care.

C3. WITHDRAWAL FROM RESEARCH PARTICIPATION

For the clinician centered data we do not anticipate any withdrawal from the study. We have been collecting data on airway interventions since 2015 as part of BAMC protocol C.2015.140 without any encounters for which a clinician asked that we cease data collection, declined participation, or asked that their data be withdrawn. However, in the event that a clinician asks to be withdrawn we will only use their CRFs that were collected up to that point. If a reason is provided, we will document such.

For the patient EMR-based data we do not anticipate any patient withdrawal as we are seeking a waiver of informed consent and HIPAA waiver and thus they will likely not be aware of the study. However, in the event that a patient does request withdrawal in writing to the PI or a study team member we will cease data collection from that point forward. Data that was already collected will still be retained for use. Since the overwhelming majority of our data comes from medical records review, we cannot make any changes, removal, or revisions to the data in the EMR system even if the patient were to request such.

C4. PRIVACY FOR SUBJECTS

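### Ventilation days are counted to unassisted breathing or death, so a device group with more early deaths can appear to need less ventilation

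*Combined protocol and SAP*

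**What the plan says.** The Appendix (Data Collection Variables) defines duration of mechanical ventilation as "Number of days from study intubation until achieved final unassisted breathing during this hospitalization or death". The entry also sets aside short procedural reintubations, ignores later outpatient data and readmissions, and adds "Information censored at hospital discharge". It gives death no separate treatment. Further down, a second row has the same name and is described only as numeric.

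Death is recorded separately as yes/no items: "Death within 1 hour of intubation", death in the ICU, and "Did the patient die before discharge from the hospital". No rule links any of them to the duration.

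B5.4 (Data Collection) labels the extracted items "Outcome data – Please see data variable collection appendix listed below". B5.8.2 (Data analysis) provides only generic tests for such variables: "normally distributed continuous variables using the Student's t-test, and non-parametric and ordinal variables using the Wilcoxon Rank sum test". Missing values are handled by pairwise deletion, and deaths are not mentioned. On the population, C1.4.3 says: "Many of the patients that we are intubating are critically ill and not expected to survive".

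**The concern.** The definition stops the clock in the same way for the best result and the worst one. In a rank test, a patient who dies within hours joins the patients who recovered fastest. Other things equal, adding early deaths to one device group moves that group towards shorter ventilation.

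This is more than a missing detail. It is a written rule which, if followed, can give a misleading result. The protocol also foresees the conditions for it: C1.4.3 expects many deaths, C8.1 names peri-intubation cardiac arrest as a known event, and the Appendix records death within the first hour. At stake is the reading of a secondary clinical result: a device with more early deaths could be credited with fewer ventilator days.

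**Working it through.** **Plan's own figure.** There is none. The documents give no expected ventilation time, mortality rate or time of death, so what follows illustrates the mechanism under assumptions.

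**Inputs from the documents**
- Volume (B5.2.2): about 200 intubations a year, 55% by video laryngoscopy, over 2 years. 200 × 0.55 × 2 = 220.
- Scoring: duration ends at unassisted breathing or at death (Appendix).
- Test: Wilcoxon rank sum at 0.05 (B5.8.2), taken as two-sided. With no difference between groups, each direction should be declared in about 2.5% of trials.

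**Assumed inputs**
- An even split, 220 / 2 = 110 per device group.
- Survivors' duration lognormal with median 4 days and log-SD 0.8, identical in both groups.
- Time to death lognormal with log-SD 0.8 and median 1 day, then varied.
- Mortality 30% in one group and higher in the other. This is the only difference between the groups.

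**Step 1: medians under the written rule.** With mortality *p* and deaths at a median of 1 day, the group median *m* solves

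(1 − p) · Φ(ln(m/4)/0.8) + p · Φ(ln(m/1)/0.8) = 0.5

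- p = 0.30, m = 2.8: 0.70 × 0.328 + 0.30 × 0.901 = 0.500.
- p = 0.40, m = 2.4: 0.60 × 0.262 + 0.40 × 0.863 = 0.502.

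The group with 10 points more mortality shows a median of 2.4 days against 2.8, although survivors are ventilated equally long in both groups.

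**Step 2: how often this is declared significant.** Simulated trials of 110 per group:

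| Mortality | Median time to death | Higher-mortality group declared shorter |
|---|---|---|
| 30% v 30% | 1 day | about 2.5% (as it should be) |
| 30% v 35% | 1 day | about 8% |
| 30% v 40% | 1 day | about 16% |
| 30% v 45% | 1 day | about 33% |
| 30% v 40% | 2 days | about 9% |
| 30% v 40% | 4 days | about 2% (no bias) |
| 30% v 40% | 8 days | below nominal; declared **longer** in about 7.5% |

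Repeat runs differ from these figures by 1 to 2 percentage points, which is simulation error.

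**Step 3: a different model.** With exponential time to unassisted breathing (median 5 days), exponential time to death (mean 1 day) and the earlier of the two scored, early deaths of 20% v 30% give medians of about 3.4 v 2.6 days. The group with more deaths is declared shorter in 16% of trials. If patients who die are instead ventilated for a mean of 15 days, deaths of 10% v 30% give medians of about 5.3 v 6.1 days, so the direction reverses here too.

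**Step 4: after the change.** The Step 2 trials were rescored with every death ranked worst. The higher-mortality group was then favoured in under 0.5% of trials in each unequal-mortality setting tabulated, whatever the time of death.

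**The case against.** The strongest case against the point has five parts.

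- **The comparison is not named.** B4 asks about first-pass success and number of attempts, and B5.8.2 adds hypoxic events. Ventilation duration is one row in a long appendix and does not enter the sample size. This stands. A reader might infer that the plan commits to a device comparison of ventilator days, but the text supports only a conditional statement: the item is labelled outcome data, and the generic tests are the only ones on offer.
- **The direction is not fixed.** A reader might infer that the rule always turns harm into apparent benefit. It does so only when deaths come earlier than recovery in survivors. The documents give no time of death, and under later deaths the bias disappears or reverses. This stands and limits the claim to early deaths.
- **The mortality gaps are assumed.** The protocol calls the devices technically equivalent and gives no reason to expect a gap of 10 to 15 points. This also stands. At 5 points the figure is about 8%.
- **Mortality would be visible anyway.** Death is recorded at three points, so a difference could be seen beside the duration. That lessens the danger, but no rule requires the two to be reported together, and the duration result would still mislead on its own.
- **Vasopressor and ICU days are a different matter.** Both are listed as plain numbers with no end-of-count rule. It would go beyond the text to say that they share the defect.

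**Conclusion.** The point holds in a limited form. The written definition scores early death like early recovery, and nothing in the analysis section corrects for it. If the variable is compared by device with the Wilcoxon test, a group with more early deaths can appear to have shorter ventilation.

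Under the stated assumptions, with deaths at a median of 1 day, the misleading declaration occurs in about 8% to 33% of trials for mortality gaps of 5 to 15 points, against a nominal 2.5%. The figure depends strongly on when patients die, which the documents do not say. The documents therefore do not show that harm will be reported as benefit, only that the rule allows it. Because the outcome is exploratory and lies outside the two research questions, this is a minor improvement and no threat to the main conclusion.

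**What to change.** 1. In B5.8.2, state that in any between-device comparison of ventilation duration every in-hospital death is ranked as the worst outcome, using the hospital-death flag already collected.
2. Report mortality by device beside that comparison.
3. Tie the second, undefined duration row to the defined one, or remove it.
4. If vasopressor or ICU days are compared by device, apply the same ranking.

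**Cost.** A change to the derivation and the analysis text, with no new data. The result becomes a composite of death and duration and is a less direct measure of ventilator use, so the raw duration can still be described, for example in survivors.

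**Why rank all in-hospital deaths.** The flag is yes/no, so it cannot separate a death on the ventilator from one after extubation. Ranking only deaths before unassisted breathing is therefore not possible from this flag. Ventilator-free days to day 28 would need dates of death, or a stated convention for status at day 28, beyond the listed variables. It is a reasonable alternative if the team will extract those, but it is not the option that needs no new data.
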